Adverse Events will be reported according to current CCHMC IRB policy and applicable federal regulations. If any serious adverse events occur, current guidelines will be followed for expedited reporting to the IRB, medical monitor, and sponsor.

- If an event meets all of the below criteria, an IND Safety Report will be generated and submitted to the FDA by the sponsor no later than 15 calendar days after the sponsor receives the safety information and determines that the information qualifies for reporting: Suspected Adverse reaction
- Serious
- Unexpected

9. Risk assessment recommendation:

- Minimal risk but with direct benefit to participants
- Minimal risk but without direct benefit to participants
- More than minimal risk, but potential direct benefit to participants
- More than minimal risk but without direct benefit to participant

XI. CONFIDENTIALITY

All records and documents pertaining to the study will be maintained by the Investigator and designee(s), and will be available for inspection by the Cincinnati Children's Hospital Institutional Review Board, the sponsor and the Medical monitor. All documents will be kept in a locked cabinet or on password protected computers in the office of the Clinical Management Research Support Core (CMRSC). Access to the files will be limited to the Principal Investigator and designees. All information provided to the investigator dealing with the study and information obtained during the course of the study will be regarded as confidential.

XII. PERIOD OF TIME ESTIMATED TO COMPLETE PROJECT AS DESCRIBED

The period of time to complete enrollment for this study is estimated to be approximately 5 years. Total time for completion of follow up is estimated to be 6 years.

XIII. FUNDING

The institution to which funding will be made: CCHMC

XIV. PAYMENT FOR STUDIES

1. Third party payers

All costs associated with the routine clinical care of patients will be the responsibility of the patient or their insurance carrier.

2. Reimbursement to participants

The patients will receive no financial compensation for participation in this research protocol. All study visits will be scheduled at the same time clinical visits are planned.

The FDA authorized cost recovery for this study. The FDA determined that the cost of Alpha Beta CD19 Depleted Stem Cell graft using Miltenyi Biotech CliniMACS Immunomagnetic Selection Device may be billed to patients and/or their insurance company.

XV. METHOD TO BE USED IN PROCURING CONSENT OF SUBJECTS

All prospective patients will have the study explained by a member of the research team. All the potential hazards and possible adverse reactions will be explained to patient/parent.

Prior to the initiation of the study, acknowledgement of the receipt of this information and the subject's freely tendered offer to participate will be obtained in writing from each subject in the study. Assent for subjects 7-10 years old will not be obtained due to the complex nature of the therapy and the limited capability of the minor to reasonably consider all the implications associated with this treatment that may be of direct benefit to the subject.

This protocol, informed consent, assent form, and any amendments to the protocol will be reviewed and approved by the CHMCC IRB prior to initiation. The study will not be initiated without the approval of the IRB.

At reaching the age of majority (typically 18 years of age), an attempt will be made to reconsent the research participant at their next visit to the CCHMC BMT clinic.

If it will be more than 12 months from the time of their 18th birthday to their next planned visit, contact via phone and via mail will be made for their consideration

to continue participation. The call and letter will explain that an attempt will be made to reconsent the research participant at their next visit. In addition, study staff contact information will be provided in case they have questions or wish to inform us of their desire to withdraw from participation prior to their next planned visit.

XVI. REFERENCES

1. Copelan EA. Hematopoietic stem-cell transplantation. *N Engl J Med.* 2006;354(17):1813-1826.
4. Petersdorf EW. Which factors influence the development of GVHD in HLA-matched or mismatched transplants? *Best Pract Res Clin Haematol.* 2017;30(4):333-335.
5. Pulsipher MA. Haplo is the new black. *Blood.* 2014;124(5):675-676.

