- [REDACTED]
- [REDACTED]

Required Observations:

[REDACTED]

Day of Graft Infusion: [REDACTED]

[REDACTED]

Post-HSCT: [REDACTED]

[REDACTED]

V. EVALUATION CRITERIA

Primary Endpoint:

The primary endpoint of the study is safety of infusion of TCR $\alpha\beta$ +/CD19+ depleted donor grafts.

We will determine the frequency and characteristics of potential infusion-related toxicity. Experience at our center using CD34+ selected stem cells has shown infusion related toxicity occurs at an incidence of <5%. We previously observed zero infusion reactions in 22 patients who received a CD34+ selected boost product as part of a CCHMC study (IRB# 2010-2344), and 2 infusion reactions among 55 infusions which were performed as part of clinical care including 1 occurrence of hypertension, and 1 occurrence of urticaria that resolved with anti-histamine administration. While there is little expectation of infusion-related toxicity, the incidence of infusion-related reactions will be recorded and evaluated.

Secondary Endpoints:

The secondary endpoints of the study are to assess engraftment and acute GVHD incidence.

Engraftment:

Engraftment and graft function are monitored on a clinical basis. Neutrophil recovery will be defined as the first of 3 consecutive days that the absolute neutrophil count is 500 cells/mcL. Platelet recovery will be defined as the first of 3 consecutive days that the platelet count is greater than 20 without any platelet cell transfusions in the previous 7 days. Initial donor-derived hematopoietic cell recovery will be defined as having 95% or greater donor-derived cells. Initial mixed donor and recipient-derived engraftment will be defined as having less

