than 95% donor-derived cells but more than 5% donor-derived cells on a first and second confirmatory engraftment study (if the second study shows $\geq 95\%$ donor cells, the patient will be classified as having donor-derived hematopoietic cell recovery). Recipient-derived hematopoietic cell recovery will be defined as having 5% or less donor-derived cells. Any patient who fails to achieve neutrophil recovery within 42 days of allogeneic HSCT, or has 5% or less donor-derived cells will be considered as having primary graft failure. We will report the cumulative incidence of achieving initial donor-derived hematopoietic cell recovery. Complete blood counts and whole blood donor chimerism studies are frequently performed on a clinical basis following allogeneic HSCT. Stable hematopoietic cell recovery at 100 Days (+/- 2 weeks) will be defined as having hemoglobin, neutrophil, and platelet counts of at least 80% of the normal range in the absence of transfusions or clinical diagnoses which may affect the counts such as hemolytic anemia, auto-immune thrombocytopenia, iron deficiency, infection or medication induced bone marrow suppression, or other clinically relevant diagnosis. Patients with these or other medical diagnoses may still be considered to have count recovery. The percentage of donor cells will be recorded at Day +100 (preferably +/- 2 weeks) and Day +100 Donor-derived hematopoietic cell recovery will be defined as having 95% or greater donor-derived cells. Day +100 mixed donor and recipient-derived hematopoietic cell recovery will be defined as having less than 95% donor-derived cells but more than 5% donor-derived cells. Recipient-derived Day +100 hematopoietic cell recovery will be defined as having 5% or less donor-derived cells. These patients will be considered as having secondary graft failure. We will report rates of successful donor-derived hematopoietic cell recovery at Day +100. Exceptions may be made for patients with Severe Combined Immune Deficiency who may reconstitute with donor-derived T cells but have autologous recovery of myeloid and other cells. For such cases we will examine results of sorted T cell chimerism studies. We will also record the incidence of any additional cell product administrations or second allogeneic HSCT. Any patient who receives a second allogeneic HSCT will be considered as having graft failure.

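### Both reported donor-derived recovery measures rest on chimerism alone, so a patient without neutrophil recovery by Day 42 can be both an engraftment success and a primary graft failure

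*Combined protocol and SAP*

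**What the plan says.** All the definitions stand in Section V, Secondary Endpoints, under Engraftment.

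- **Initial success.** "Initial donor-derived hematopoietic cell recovery will be defined as having 95% or greater donor-derived cells". It is a reported result: "We will report the cumulative incidence of achieving initial donor-derived hematopoietic cell recovery".
- **Day +100 success.** "Day +100 Donor-derived hematopoietic cell recovery will be defined as having 95% or greater donor-derived cells". It is also reported: "We will report rates of successful donor-derived hematopoietic cell recovery at Day +100".
- **Primary graft failure.** This class takes in the following: "Any patient who fails to achieve neutrophil recovery within 42 days of allogeneic HSCT, or has 5% or less donor-derived cells". The two limbs are joined by *or*, and the first makes no reference to chimerism.
- **Count-based terms.** "Neutrophil recovery will be defined as the first of 3 consecutive days that the absolute neutrophil count is 500 cells/mcL". Platelet recovery has its own definition. A further term is set for Day 100: "Stable hematopoietic cell recovery at 100 Days (+/- 2 weeks) will be defined as having hemoglobin, neutrophil, and platelet counts of at least 80" (the last figure is a percentage of normal), with some discretion for patients who have other diagnoses. None of these terms is made a condition of either success measure.

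The same section lists primary graft failure among the events for Day +100 event-free survival. Section VII.2 plans cumulative incidence curves for engraftment and acute GVHD and names death as the competing event.

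**The concern.** Engraftment is the first of the secondary objectives in Section I. A reader of the final report will take a rate of donor-derived hematopoietic cell recovery to mean that the graft is working. As defined, the rate says only whose cells are present. A patient whose few circulating cells are all of donor origin, but whose neutrophils have not recovered by Day 42, meets the success definition and the failure definition together.

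At stake is the internal consistency of the secondary results. The same patient would raise the engraftment incidence and lower event-free survival in one report, and two analysts applying the written rules could classify that patient differently.

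**Working it through.** No figure in the plan needs reproducing: the documents state no expected engraftment rate, and no test or sample size rests on one. The check applies the written rules to each combination of the two facts that they use.

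**Step 1. Rules (Section V, Engraftment).** Let A = neutrophil recovery by Day 42 (yes/no) and C = donor-derived cells (%).

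- Initial donor-derived recovery: C ≥ 95.
- Mixed: 5 < C < 95 (confirmed on a second study).
- Recipient-derived: C ≤ 5.
- Primary graft failure: A = no, or C ≤ 5.

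**Step 2. Apply them.** The values tried for C were 2, 5, 50, 94, 95 and 100, giving 12 combinations with A.

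| Neutrophil recovery by Day 42 | C = 2, 5 | C = 50, 94 | C = 95, 100 |
|---|---|---|---|
| Yes | recipient; graft failure | mixed; no failure | donor-derived recovery; no failure |
| No | recipient; graft failure | mixed; graft failure | **donor-derived recovery and graft failure** |

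Two of the 12 combinations (no neutrophil recovery, C = 95 or 100) are a reported success and a primary graft failure at once. With neutrophil recovery there is no such overlap.

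**Step 3. Look for a rule that separates them.** None was found. The provision on a second chimerism study moves a patient into donor-derived recovery on the chimerism result alone. The exception for severe combined immune deficiency (SCID) concerns which cell compartment is tested and adds no count condition. Section VII.2 does not list graft failure as a competing event.

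**Step 4. Day +100.** The Day +100 definition is again C ≥ 95 alone, so an earlier primary graft failure can become a Day +100 success. Other rules narrow this route. The patient must be alive and still at 95% or more, any second allogeneic HSCT counts as graft failure (Section V), and receipt of a second stem cell product takes the patient off study (Section VI).

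**Step 5. Size per patient.** With the planned 80 patients (Section IV.1a), and as a crude proportion, one overlap patient contributes 1/80 = 1.25 points; two contribute 2/80 = 2.5 and four contribute 4/80 = 5.0. These counts are illustrations.

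**Step 6. What bounds the number.** For the initial measure, the overlap is by construction a subset of primary graft failures. Two studies in Table 1 of Section III separate primary from secondary failure: 2/23 = 8.7% and 2/37 = 5.4%. If those rates carried over, which is an assumption, there would be 80 × 2/23 ≈ 7.0 or 80 × 2/37 ≈ 4.3 primary failures of every kind. Table 1 does not split them by chimerism, so the overlap could lie anywhere from none up to that total.

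**The case against.** The other side has several fair points.

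- **Donor, mixed and recipient describe lineage.** Reporting the origin of the cells apart from graft function is legitimate, and the words recovery and successful may presuppose counts. This stands as a likely intention. The operative definitions, however, do not say it, and the section defines count recovery separately without linking the two.
- **Count-based curves may be produced as well.** Section VII.2 plans curves for engraftment without choosing a definition. That is so, but it would leave the two named measures as they are.
- **Graft failures remain visible.** They are events in event-free survival. A reader might infer that the plan hides failures; it does not. What remains is that two reported results disagree about the same patient.
- **Engraftment drives no decision.** This is a single-arm descriptive study whose primary endpoint is infusion safety. This stands, and it limits the weight of the point.

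Two stronger readings are tempting and are not supported. First, a reader might infer that both rates are overstated by several points, using an assumed frequency of poor graft function with full donor chimerism. That group is wider than the overlap: it includes patients with neutrophil recovery but weak platelets or transfusion need, who are not primary graft failures. The documents give no frequency for either group, and the Day +100 overlap is narrower than the initial one. Second, a reader might infer that the time-to-engraftment curve is shifted early because a chimerism reading can precede count recovery. No text dates the endpoint at the chimerism draw, and the observation schedule is redacted, so a shift in either direction is unproven.

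**Conclusion.** The definitions are wrong as written, with limited effect. The stated rules place a patient with 95% or more donor cells and no neutrophil recovery by Day 42 in a reported success category, in primary graft failure and among the Day +100 event-free survival events, with nothing to resolve the conflict. This follows from the wording and does not depend on how often it happens.

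The size is 1.25 points per such patient on the initial rate. The same patient counts at Day +100 only if alive, still at 95% or more and without a second graft. The 1.25 assumes that all 80 patients are in the denominator; it would be larger if the Day +100 rate were taken over fewer patients. The number of such patients is unknown, so no total bias is claimed. The consequence is confined to secondary descriptive results.

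**What to change.** **Initial measure.** Adopt one of two wordings.

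1. Count initial donor-derived recovery only when neutrophil recovery by Day 42 and 95% or more donor cells are both met. State the event date, for example the later of the two, and say how patients who never become neutropenic are handled. Section IV allows transplant without conditioning, so such patients may occur.
2. State that primary graft failure takes precedence over donor-derived recovery and is a competing event in the cumulative incidence. Precedence must be explicit: if a reading of 95% or more obtained before Day 42 had already been counted as the event, adding a competing event at Day 42 would not remove it.

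**Day +100 measure.** Do not count a patient with prior primary graft failure as a success. Report Day +100 donor chimerism cross-tabulated with the count-based stable recovery category that Section V already defines, so that full donor chimerism with poor counts is visible. Making the 80%-of-normal criteria a condition of success is not advised, because their discretionary clause would bring case-by-case judgement into the endpoint.

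Keep the SCID exception.

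**Cost.** Only the endpoint wording and one extra table change; counts and chimerism are already obtained clinically. The success rates may be slightly less favourable. A patient whose neutrophils recover after Day 42 would not be a Day +100 success, although the cross-tabulation would still show that patient's counts and chimerism.

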Patients attending the CCHMC bone marrow transplant (BMT) clinic who meet the eligibility criteria will be offered the opportunity to participate in this research study. The study is open to all participants regardless of gender or ethnicity.

2a. Inclusion Criteria

Any patient requiring an allogeneic HSCT who lacks an HLA-genotypically matched related donor. Genotypically matched related donors are allowed when there is a clinical desire to avoid the use of GVHD prophylaxis medications.

2b. Exclusion Criteria

Prior allogeneic transplant with active acute or chronic GVHD, or life-threatening infection. Patients with a prior history of allogenic transplant without active GVHD or life-threatening infection can be considered.

2c. Patients Requiring Second Allogeneic HCT or Additional Aliquots of Stored Hematopoietic Stem Cell Product

Patients may receive additional TCRA/b CD19 depleted product(s) if clinically indicated.

3. Randomization

Not applicable.

4. Procedures

Pre-Infusion Patient Evaluation:

Patients enrolled on this protocol will undergo evaluation for disease status and organ function per institutional HSCT guidelines prior to starting conditioning regimen.

Donor Selection:

Transplant donors will be selected based on institutional guidelines/SOPs.

Treatment Plan:

[REDACTED]

[REDACTED]

Informed Consent:

Informed consent will be obtained for each study participant (stem cell transplant recipient) and/or parent or legal guardian as appropriate. The study will be explained to the study subject in lay terms, in their native language. The informed consent process will require written consent by the patient (if ≥ 18 yrs of age) or parent/legal guardian.

The investigator will be available to answer any questions that the patient or caregiver may have regarding procedures, risks and alternatives. The signed consent form will be maintained in the study subject's chart with a copy being placed in the patient's medical record.

Preparative therapy:

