We will report the Day +100 event-free survival of patients where an event is defined as death, primary graft failure, autologous recovery (<5% donor-derived cells in whole blood or in the cellular compartment of interest, i.e. T cells in patients with SCID), secondary graft failure, receipt of an additional hematopoietic cell

product other than for control of infection (Donor lymphocyte infusion or Virus-Specific T cell infusion), and second allogeneic HSCT.

Acute GVHD:

Clinical assessments for acute GVHD are frequently performed using Modified Glucksberg Criteria as in Appendix 1. We will collect clinical information regarding incidence and severity of acute GVHD. We will report the Day +100 cumulative incidences of acute GVHD grades II-IV and III-IV.

Chronic GVHD:

Clinical assessments for chronic GVHD are also frequently performed using NIH Consensus criteria. We will report the 1 year cumulative incidences of chronic GVHD.

GVHD-Free Survival:

Based on the presence or not of acute or chronic GVHD at 1 year, we will report GVHD-free survival at 1 year.

VI. OFF STUDY CRITERIA/CRITERIA FOR WITHDRAWING SUBJECTS

Subjects (or parents or legal guardians) have the right to withdraw from the study at any time and for any reason without prejudice to his or her future medical care by the physician or the institution.

Any subject who withdraws consent to participate in the study will be removed from further treatment and/or study observation immediately upon the date of request. The subject will be followed for safety purposes for at least 1 week after infusion of the stem cell product.

Criteria for Removal from Protocol Therapy:

- Patient withdrawal from protocol therapy

Off Study Criteria:

- a) Death
- b) Receipt of a second stem cell product
- c) Lost to follow-up

VII. STATISTICAL CONSIDERATIONS

1. Sample Size and Study Duration:

We chose a sample size of 80 patients based on estimates of patient need for access to T cell depleted grafts over 3-5 years at our Institution. All patients will be followed for primary and secondary endpoints for at least 100 Days following allogeneic HSCT, and 1 year data will be collected regarding survival and presence or absence of acute or chronic GVHD.

2. Statistical Considerations for Data Analysis:

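### The Day +100 donor-derived recovery rate can overstate engraftment of the initial graft, because patients given a further cell product are not separated out

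*Combined protocol and SAP*

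**What the plan says.** Section V (Engraftment) sets the Day +100 outcome by chimerism: "Donor-derived hematopoietic cell recovery will be defined as having 95% or greater donor-derived cells". The only qualification is an exception for severe combined immune deficiency, where sorted T cells may be examined instead. The plan then says: "We will report rates of successful donor-derived hematopoietic cell recovery at Day +100". It states no denominator.

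Further cells are dealt with in four other places:

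- Section IV.2c: "Patients may receive additional TCRA/b CD19 depleted product(s) if clinically indicated". Its heading also covers stored aliquots.
- Section V (Engraftment): "We will also record the incidence of any additional cell product administrations or second allogeneic HSCT", followed by "Any patient who receives a second allogeneic HSCT will be considered as having graft failure".
- Section V, Day +100 event-free survival: the events include a further hematopoietic cell "product other than for control of infection (Donor lymphocyte infusion or Virus-Specific T cell infusion), and second allogeneic HSCT".
- Section VI, Off Study Criteria: a patient who is given a second stem cell product goes off study. Section VII.1, however, has every patient followed for the primary and secondary endpoints for a minimum of 100 days after transplant.

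Section VII.2 names death as the only competing event for the engraftment curves.

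**The concern.** Engraftment comes first among the secondary objectives in Section I, and a reader will take the Day +100 rate as evidence of what the depleted graft does. If a patient with poor graft function receives more cells and then reads 95% or more, the result reflects the initial graft and the added cells together. The plan recognises this elsewhere: a second transplant is scored as graft failure, and event-free survival counts a further product not given for infection as an event. The recovery rate carries over the first rule but not the second.

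Graft failure is not a remote possibility in this setting. Four of the five series in Table 1 (Section III) report it: (2+2) + (2+8) + 5 + 2 = 21 failures among 23 + 37 + 41 + 80 = 181 patients, or 11.6% (exact 95% CI 7.3% to 17.2%). These are graft failures, not rescues that ended at 95% or more donor cells, so they show only that the situation can arise.

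**Working it through.** The plan attaches no target, threshold or power to this rate, and Section VII.1 bases the 80 patients on expected need. There is no figure to reproduce. The check has two parts.

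**Classification.** Take a patient who receives a further product before Day +100, short of a second transplant, and reads 95% or more donor cells at Day +100.

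1. Under the Day +100 definition in Section V the patient is a success. Nothing there depends on how the value was reached.
2. The second-transplant rule does not apply.
3. Recording the product, as Section V requires, does not alter the score.
4. If the product is a stem cell aliquot, Section VI may take the patient off study, while Section VII.1 keeps all patients in follow-up to at least Day +100. The patient could be a success, missing or excluded.
5. If the product is donor lymphocytes, it is arguably not a stem cell product. The patient then stays on study and the success reading applies most directly.

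**Size.** Inputs: N = 80 (Sections IV.1a and VII.1). S = 64 patients reaching 95% or more without further cells is assumed for illustration. The number k of patients as described above is not in the documents, and 1 to 12 is assumed.

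- Not credited to the initial graft: S/N = 64/80 = 80.0%
- Scored as written: (S + k)/N
- Dropped as off study: S/(N − k)

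| k | Scored as written | Dropped |
|---|---|---|
| 1 | 65/80 = 81.3% | 64/79 = 81.0% |
| 2 | 66/80 = 82.5% | 64/78 = 82.1% |
| 4 | 68/80 = 85.0% | 64/76 = 84.2% |
| 8 | 72/80 = 90.0% | 64/72 = 88.9% |
| 12 | 76/80 = 95.0% | 64/68 = 94.1% |

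The excess as written is k/80, or 1.25 points per patient whatever S is. At the 73 patients named in Section VII.3 it would be 1/73 = 1.37 points. Dropping gives a slightly smaller shift here, but that shift arises for every dropped recipient outside S, whatever the Day +100 reading. Both shifts are zero if k is zero.

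**The case against.** The strongest reply is that the plan already makes rescue visible. A second transplant is graft failure. Primary graft failure has its own definition ("Any patient who fails to achieve neutrophil recovery within 42 days of allogeneic HSCT, or has 5% or less donor-derived cells"). The incidence of further products is recorded, and event-free survival penalises those not given for infection. Chimerism and event-free survival measure different things, so one patient may be scored differently on each without error. This is right, and it limits the consequence to one descriptive rate. It does not remove the problem: event-free survival is a composite with death and graft failure, and an overall count of further products does not show how many recipients sit among the successes.

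Four stronger readings are tempting, and the documents do not support them.

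- A reader might infer that the rate will be overstated. No sentence says that rescued patients are successes. The result follows from an unqualified definition, needs at least one such patient, and may be changed by the off-study rule. Treatment and post-transplant text is redacted, so related handling there cannot be excluded.
- A reader might infer that the bias always favours the graft. Section IV.2c does not restrict further product to falling chimerism. A patient already at 95% or more who receives cells for low counts is fairly called a donor-derived recovery, and scoring that patient simply as a failure would understate the graft.
- A reader might infer that donor lymphocytes for falling chimerism are an event in event-free survival. The parenthesis ("product other than for control of infection (Donor lymphocyte infusion or Virus-Specific T cell infusion") may exempt all such infusions or only those given for infection. The visible text does not describe their use for chimerism.
- A reader might put the inflation at 2.5 to 15 points, by assuming that 5% to 15% of patients are rescued and half to all of them restored. Neither share is in the documents, and Table 1 does not supply them.

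**Conclusion.** The concern holds as a conditional one. Read as an engraftment rate for the initial graft, Day +100 donor-derived recovery can be overstated, because a further cell product short of a second transplant does not affect the scoring. Dropping recipients as off study also moves the rate upward. The firm figure is 1.25 percentage points per affected patient at N = 80. The total cannot be derived, since the number of such patients is not given and may be zero; the tabulated rates rest on the assumed S = 64 and k. No hypothesis test or decision rule depends on this rate, so the issue is how the result will be read, not the validity of the trial.

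**What to change.** In Section V (Engraftment):

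1. Report Day +100 donor-derived recovery over all infused patients, including those who have gone off study.
2. Count as success of the initial graft only 95% or more donor cells with no prior further hematopoietic cell product, other than one given for infection control, in line with the event-free survival definition.
3. Show 95% or more donor cells after a further product as a separate category, and note whether the patient had already reached 95% before that product. This deals with the patient treated for low counts, and a reader can add the categories together if an overall figure is wanted.

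Sections IV.2c, V, VI and VII.1 should also be reconciled on whether a recipient of a further product is off study and how Day +100 data are then obtained. The event-free survival parenthesis should say whether it exempts all donor lymphocyte infusions or only those given for infection.

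The cost is a few sentences. Administration of further products is already to be recorded, and Day +100 chimerism is already collected. The recovery rate may look slightly less favourable.

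### Every second allogeneic HSCT is scored as graft failure, so an engrafted patient retransplanted for relapse is misclassified

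*Combined protocol and SAP*

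**What the plan says.** The Engraftment text in Section V (Evaluation Criteria) builds graft failure from two measurements. Primary graft failure applies to "Any patient who fails to achieve neutrophil recovery within 42 days of allogeneic HSCT, or has 5% or less donor-derived cells". Secondary graft failure is donor cells at 5% or below at the Day +100 assessment. One exception is given: "Exceptions may be made for patients with Severe Combined Immune Deficiency who may reconstitute with donor-derived T cells", for whom sorted T cell chimerism is examined.

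Two sentences on further transplants follow. The first is a recording rule: "We will also record the incidence of any additional cell product administrations or second allogeneic HSCT". The second is a classification rule: "Any patient who receives a second allogeneic HSCT will be considered as having graft failure". Neither mentions the reason for the second transplant, and the second sets no chimerism condition and no time limit.

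Other parts of the protocol bear on this rule:

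- Section I covers malignant and non-malignant disorders. Section IV.2c, whose title refers to second allogeneic transplants, states: "Patients may receive additional TCRA/b CD19 depleted product(s) if clinically indicated". It is not limited to failed engraftment.
- The engraftment results to be reported are the cumulative incidence of initial donor-derived recovery and the Day +100 rate: "We will report rates of successful donor-derived hematopoietic cell recovery at Day +100".
- The Day +100 EFS event list names primary and secondary graft failure, and ends with an additional cell "product other than for control of infection (Donor lymphocyte infusion or Virus-Specific T cell infusion), and second allogeneic HSCT". Relapse is not an EFS event.
- Section X.8 (Adverse Event Reporting) excludes graft failure from adverse events because it is captured as an endpoint.
- Section VI makes receipt of a second stem cell product an off-study criterion.

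**The concern.** The closing sentence replaces a measured outcome with a treatment received. For a second transplant given because the first graft failed, the two agree. For one given because leukaemia returned in a patient whose graft is working, they do not: the patient has donor-derived recovery by the plan's criteria and graft failure by the rule.

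Engraftment is a named secondary objective. If relapse treatment is folded into the graft-failure count, that count no longer describes how the depleted graft performed. The visible plan gives no way to separate the cases afterwards, because it records the incidence of second HSCT without asking for its reason.

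**Working it through.** The documents state no graft-failure rate, target or power for this trial, so there is no figure to reproduce. The check is a reading of the rules, followed by an illustration of size.

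**Step 1: apply the rules to one patient.** Take a leukaemia patient with neutrophil recovery before Day 42 and 95% or more donor cells, who relapses and receives a second allogeneic HSCT.

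| Rule | Result for this patient |
|---|---|
| Neutrophil recovery within 42 days | Achieved, not graft failure |
| Donor cells 5% or less (primary or secondary) | Not met, not graft failure |
| SCID exception | Does not apply |
| Initial donor-derived recovery (95% or more) | Success |
| Second-HSCT sentence | Graft failure |

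Only the last row gives graft failure, and no text exempts relapse.

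**Step 2: find which results move.**

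- Initial and Day +100 donor-derived recovery are defined by donor percentage. The second-HSCT sentence does not enter, so they do not change.
- Total Day +100 EFS counts a second HSCT as its own event. The patient is an event once, with or without the graft-failure label, so the total does not change.
- The graft-failure count rises by one.
- In a breakdown of EFS events by cause, this patient can be listed under graft failure although the graft had not failed.

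**Step 3: size if cases are counted without a time limit.** Table 1 (Section III) gives 19 relapses among 80 patients in the ALL/AML haploidentical series, or 19/80 = 23.75%. Let m be the malignant share of the 80 planned patients and f the share of relapsed patients retransplanted. Both are assumptions, since the documents give neither.

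Added graft failures = 80 × m × 0.2375 × f

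| m | Relapses | f = 10% | f = 25% | f = 50% |
|---|---|---|---|---|
| 25% | 4.75 | 0.5 | 1.2 | 2.4 |
| 50% | 9.5 | 0.95 | 2.4 | 4.75 |
| 75% | 14.25 | 1.4 | 3.6 | 7.1 |

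These figures are long-run: the survival entry for that series is at 5 years.

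**Step 4: size within the planned window.** Section VII.1 follows primary and secondary endpoints for at least 100 days, with 1-year data on survival and GVHD. Section X.8 follows engraftment and EFS through Day +100. To be miscounted in that window, a patient must engraft, relapse and be retransplanted by about Day +100. At m = 50%, two such patients would mean that 2/9.5 = 21% of all long-run relapses had both occurred and been retransplanted by then. A range of 0 to 2 of 80 (0 to 2.5 percentage points) is therefore a reasonable working assumption, not a figure from the documents.

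**The case against.** The strongest reply is that nothing the plan promises to report is affected. It lists donor-derived recovery and EFS, and no graft-failure rate. Both listed engraftment results and total EFS are untouched, as Step 2 shows. This stands as a limit on the consequence. It does not remove the point, because Section X.8 treats graft failure as a captured endpoint, and primary and secondary graft failure are named EFS components.

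A second reply is that a treatment-based rule is simple, needs no judgement of indication, and errs against the product. That is a fair reason for some such rule. It also catches patients retransplanted before the 42-day criterion has run out. It does not justify applying the rule to patients whose grafts are working.

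A third reply is that second transplants are recorded anyway. Their incidence is. The case report form is not among the documents, so whether it captures the reason is unknown.

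A reader might infer three stronger points that the documents do not support:

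- *That the graft-failure rate could double.* This needs long-run relapse counts, an assumed retransplant share and a low baseline. Table 1 also shows 4/23 and 10/37 graft failures in the non-malignant series. With half the patients malignant, the baseline runs from 40 × 4/23 + 40 × 2/80 = 8.0 to 40 × 10/37 + 40 × 5/41 = 15.7 patients. Two extra cases would add 25% to 13%.
- *That results would not be comparable with Table 1.* The table gives graft-failure counts without definitions, so comparability cannot be judged either way.
- *That success and failure in the same patient is itself a contradiction.* Secondary graft failure can properly follow initial recovery. The fault is the label given to a functioning graft.

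**Conclusion.** The concern holds as a misclassification in a stated rule. A second allogeneic HSCT for relapse in a patient with donor-derived recovery is coded as graft failure, against the plan's own neutrophil and chimerism criteria. The graft-failure count and the attribution of EFS events are affected. The primary endpoint, the TRM stopping rule, total Day +100 EFS and the donor-derived recovery rates are not.

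The likely size is 0 to 2 of 80 patients within Day +100, by assumption. It could be larger, up to about 7 under the most extreme combination in Step 3, if graft failure is counted without a time limit as the sentence allows. The off-study criterion and the Day +100 follow-up make such late counting less likely but do not exclude it.

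**What to change.** Replace the sentence with:

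> A second allogeneic HSCT is counted as graft failure only if the patient met the neutrophil or donor-chimerism criteria for primary or secondary graft failure (sorted T cell chimerism in SCID) at the last assessment before it. A second HSCT for relapse or another reason is reported separately with its indication, date and last chimerism result.

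State also that a patient retransplanted before Day 42 without neutrophil recovery counts as graft failure, so that narrowing the rule does not lose those cases. Leave second allogeneic HSCT in the EFS event list.

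The cost is one revised sentence, one extra data item (indication, kept with the date and last chimerism result) and a small judgement on indication, which the recorded chimerism result makes checkable. The change concerns endpoint classification only and does not touch patient care.
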